Nonserious AEs should be followed to resolution or stabilization, or reported as SAEs if they become serious. Follow-up is also required for nonserious AEs that cause interruption or discontinuation of study drug and for those present at the end of study treatment as appropriate. All identified nonserious AEs must be recorded and described on the nonserious AE page of the study record.

256 Completion of supplemental study records may be requested for AEs and/or laboratory 257 abnormalities that are reported/identified during the course of the study.

958 Laboratory Test Result Abnormalities

The following laboratory test result abnormalities should be captured on the nonserious AE study record page or SAE Report Form as appropriate:

• Any laboratory test result that is clinically significant or meets the definition of an SAE

- Any laboratory test result abnormality that required the subject to have study drug
 discontinued or interrupted
- Any laboratory test result abnormality that required the subject to receive specific corrective
 therapy.
- 966

967 It is expected that wherever possible, the clinical rather than laboratory term would be used by968 the reporting investigator (e.g., anemia versus low hemoglobin value).

969

970 Pregnancy

971 If, following initiation of the investigational product, it is subsequently discovered that a 972 study subject is pregnant or may have been pregnant at the time of investigational product 973 exposure, including during at least 6 half-lives after product administration, the investigational 974 product will be permanently discontinued.

Protocol-required procedures for study discontinuation and follow-up must be performed on
the subject unless contraindicated by pregnancy (e.g., x-ray studies). Other appropriate
pregnancy follow-up procedures should be considered if indicated.

The investigator must immediately notify Novo Nordisk (or designee) Medical Monitor of this event and complete and forward a Pregnancy Surveillance Form to Novo Nordisk (or designee) within 24 hours and in accordance with SAE reporting procedures described in Section 1A.

Follow-up information regarding the course of the pregnancy, including perinatal and neonatal outcome and, where applicable, offspring information must be reported on the Pregnancy Surveillance Form.

984 Overdose

An overdose is defined as the accidental or intentional administration of any dose of a product that is considered both excessive and medically important. All occurrences of overdose must be reported as an SAE (see Section 1A for reporting details.).

988 1. Potential Drug Induced Liver Injury (DILI)

989 Wherever possible, timely confirmation of initial liver-related laboratory abnormalities 990 should occur prior to the reporting of a potential DILI event. All occurrences of potential DILIs, 991 meeting the defined criteria, must be reported as SAEs (see Section 1A for reporting details).

992 Potential drug induced liver injury is defined as:

993 994 AT (ALT or AST) elevation > 3 times upper limit of normal (ULN)

- AND
- 995Total bilirubin > 2 times ULN, without initial findings of cholestasis (elevated serum996alkaline phosphatase),
- 997 AND
- No other immediately apparent possible causes of AT elevation and hyperbilirubinemia,
 including, but not limited to, viral hepatitis, pre-existing chronic or acute liver disease, or
 the administration of other drug(s) known to be hepatotoxic.
- 1001

1002 2. Adverse Events of Special Interest

1003 Certain serious adverse events are informative as single cases because they are uncommon 1004 and are known to be strongly associated with drug exposure (in accordance with the reporting 1005 obligations of 21 CFR 312.32). The occurrence of even one case of such adverse events would 1006 meet the definition of *suspected adverse reaction* (i.e., there is a reasonable possibility that the 1007 drug caused them).

1008 In this study, the following adverse events are to be reported to Novo Nordisk, regardless of 1009 whether these reports are classified as serious or unexpected:

- 1010 1. liver test abnormalities accompanied by jaundice or hyperbilirubinemia
- 1011 2. opportunistic infections
- 1012 3. pancreatitis
- 1013 4. anaphylaxis
- 1014 5. angioedema
- 1015 6. Steven-Johnson's Syndrome
- 1016

When one of these events meets the criteria for a serious adverse event, report the event using
SAE reporting procedures. When one of these events does not meet the criteria for a serious
adverse event, report the event within 24 hours as a non-serious event.

1020 3. Other Safety Considerations

1021 Any significant worsening noted during interim or final physical examinations, 1022 electrocardiogram, x-ray filming, any other potential safety assessment required or not required 1023 by protocol should also be recorded as a nonserious or serious AE, as appropriate.

- 1024
- 1025 Discontinuations

1026 The reason for a subject discontinuing from the study will be recorded in the patient chart. 1027 A discontinuation occurs when an enrolled subject ceases participation in the study, regardless 1028 of the circumstances, prior to completion of the protocol. The investigator must determine the 1029 primary reason for discontinuation. Withdrawal due to adverse event will be distinguished from 1030 withdrawal due to insufficient response according to the definition of adverse event noted 1031 earlier. The final evaluation required by the protocol will be performed at the time of study discontinuation. The investigator will record the reason for study discontinuation, provide or 1032 1033 arrange for appropriate follow-up (if required) for such subjects, and document the course of the subject's condition. They will also to be reported to Woman's Hospital Foundation 1034 1035 Institutional Review Board at [contact] and Woman's Health Research Department at 1036 [contact].

1037

1038

Subjects MUST discontinue investigational product for any of the following reasons:

- Withdrawal of informed consent (subject's decision to withdraw for any reason).
- Any clinical adverse event, laboratory abnormality, or intercurrent illness, which, in
 the opinion of the investigator, indicates that continued participation in the study is
 not in the best interest of the subject.
- 1042 Pregnancy
- 1043oInstruct subjects to contact the investigator or study staff immediately if they1044suspect they might be pregnant (e.g., missed or late menstrual period) at any1045time during study participation. Institutional policy and local regulations should1046determine the frequency of study pregnancy tests for subjects enrolled in the1047study.
- 1048oThe investigator must immediately notify Novo Nordisk if a study subject1049becomes pregnant.
- Loss of ability to freely provide consent through imprisonment or involuntary incarceration for treatment of either a psychiatric or physical (e.g., infectious disease) illness.

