Hyperandrogenism (HA) comprises the biochemical hallmark of PCOS with elevated free testosterone levels accounting for the majority of the abnormal laboratory findings in women with oligomenorrhea. Hyperandrogenism has also been linked with several components of metabolic syndrome. Metabolic syndrome (MetS) is characterized by a cluster of risk factors including hypertension, elevated triglycerides, low high-density lipoprotein cholesterol, glucose intolerance, and obesity, which also identifies those at risk for cardiovascular disease. Insulin 111 resistance with subsequent hyperinsulinemia plays a major role in the development of MetS. The association of carbohydrate metabolism abnormalities with androgen excess disorders, 112 113 particularly PCOS, is a well-defined entity. In particular, androgen excess in PCOS may contribute to increased visceral fat, decreased lipolysis in subcutaneous fat, reduced insulin 114 115 sensitivity in adipose tissue and skeletal muscle, decreased high-density cholesterol (HDL-C) 116 levels, and increased low-density lipoprotein cholesterol (LDL-C) levels. Some studies have 117 indicated a positive association between MetS and HA in women with PCOS. Metabolic 118 syndrome and its individual components are common in PCOS, particularly among women with 119 the highest insulin levels and body mass index (BMI). In women with PCOS, there is an insulin 120 post-binding defect in receptor signaling due to increased insulin receptor substrate-1 serine 121 phosphorylation that selectively affects metabolic, but not mitogenic pathways in classic insulin 122 target tissues and in the ovary. Hyperandrogenism per se may have a role in the higher prevalence of glucose intolerance in these patients. In the United States, 33–47% of women 123 124 with PCOS have MetS, a rate two to three times higher than that of age-matched healthy 125 women without PCOS. An estimated 30–40% of PCOS patients have IGT and 7.5–10% have T2D. 126 Studies suggest that the annual progression rate from normal glucose tolerance to IGT and from 127 IGT to T2D in women is substantially enhanced among women with PCOS, with the highest risk 128 in women who are also obese and have a family history of type 2 diabetes.

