148 There is considerable heterogeneity in clinical studies among women with hyperandrogenism and there could be multiple clinical phenotypes, even in a single patient at 149 150 different ages. Obesity significantly affects the circulating concentrations of total testosterone and SHBG. Body fat excess, particularly visceral fat accumulation, is another common finding in 151 152 these women regardless of weight and even at a young age. Literature data consistently confirm 153 that up to 80% of PCOS subjects are overweight or obese, with a typical central distribution of 154 adipose tissue. It has been hypothesized that body fat could have a direct role in determining 155 insulin resistance and possibly and rogen hypersecretion in these women, by mechanisms such 156 as increased lipolysis, abnormal adipokine secretion, and altered steroid hormone metabolism. Body weight status was the major factor determining the risk of IGT and MetS in women with 157 158 PCOS. However, the intricate interrelationships between body fat excess, insulin resistance, and hyperandrogenism make it difficult to assess the specific role of each of them. Obesity-related 159 160 insulin resistance and resulting hyperinsulinemia may cause a decreased SHBG and an increased 161 ovarian androgen production, both of which contribute to the hyperandrogenism. However, this 162 may form a vicious circle as hyperandrogenism may also contribute to the insulin resistance by 163 increasing free fatty acid flux to the liver and muscle through visceral lipolysis and, in addition, by altering muscle structure toward less insulin-sensitive muscle fibers. Indeed, obese women 164 with PCOS have more profound IR or T2D, gestational diabetes, dyslipidemia and risk of 165 cardiovascular disease and greater level of androgens due to low levels of SHBG. Ethnicity, 166 167 genetic background, personal and family history, degree of obesity must all be taken into account because they might aggravate or even trigger metabolic disturbances women with 168 PCOS. 169

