185 A great deal of attention has been given to the metabolic disturbances that accompany PCOS as well as these disturbances later in life. The growing body of evidence linking PCOS to an 186 187 inherited resistance to insulin action, aggravated by lifestyle problems such as obesity, poor diet and physical inactivity has led to trials of drug therapies in patients with PCOS. Over the last 188 189 years, considering the importance given to insulin resistance in the pathogenesis of the 190 syndrome, clinical studies have focused on insulin sensitizing drugs for the treatment of women 191 with PCOS, with metformin being the drug most extensively studied in this syndrome. Although 192 no antidiabetic agents have US Food and Drug Administration approval for the treatment of 193 PCOS, metformin was preferred due to the fact that it had the safest risk-benefit ratio, and could 194 cause weight loss, while thiazolidinediones increased weight as a result of fluid retention. Metformin acts by decreasing hepatic gluconeogenesis and free fatty acid oxidation while 195 increasing peripheral glucose uptake. Early studies in PCOS suggested that metformin indirectly 196 reduces insulin levels, dyslipidemia and systemic inflammation; however, recent placebo-197 198 controlled trials failed to demonstrate significant metabolic benefit. Considerable variability in 199 the metabolic responses to metformin has been observed in women with PCOS, attributable to several potential factors such as different doses of the drug and genetic background. While 200 201 metformin is not a weight loss drug it is possible that the weight loss that often accompanies 202 protracted metformin therapy may account for some of the beneficial effects observed in many studies. Weight loss has been claimed to be a beneficial secondary effect of extended release 203 204 metformin but the effect is not very consistent. Metformin has inconsistently demonstrated weight reduction. In addition, metformin has been shown to have no clinically significant effect 205 in reducing abdominal adiposity. Interestingly, most studies have not found any beneficial 206 207 effects of metformin treatment in obese patients with PCOS. Irrespective of treatment group (after adjustment for baseline BMI and age), only weight loss, but not the use of metformin, was 208 209 associated with a significant improvement in metabolic and reproductive function in obese women with PCOS. Furthermore, a number of studies have substantiated the view that obesity 210 211 may reduce the benefit of metformin treatment.

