593 A fat distribution index below 0.9 indicates a gynoid fat distribution, i.e. the fat mass of the 594 lower body surpassed the fat mass of the upper body. A fat distribution index >1.1 defines an 595 android fat distribution. In this case the amount of fat tissue of the abdominal region surpassed 596 the fat mass of the lower body. An FDI between 0.9 and 1.1 is classified as an intermediate 597 stage of fat distribution. We will use the FDI for further quantification of the fat distribution compared to the widely used waist to hip ratio. The WHR describes body shape and silhouette 598 599 while the FDI provides the quantitative amount of fat distribution. Nevertheless we have to be aware that the FDI describes not the ratio of abdominal fat to gluteal-femoral fat, but the ratio 600 601 between upper body fat, including abdominal fat and breast fat mass, and lower body fat.

602 Following baseline screening, eligible patients will be randomly assigned, in a 2:1 ratio, to receive once-daily subcutaneous injections of liraglutide, starting at a dose of 0.6 mg with 603 604 weekly 0.6-mg increments to 3.0 mg, or placebo; both groups will also receive counseling on lifestyle modification. All subjects will be allocated to one of these 2 groups based on computer-605 606 generated random numbers using a block randomization method. The randomization list will be 607 generated at the study site by the unblinded research assistant. Liraglutide and placebo will be provided in pre-filled pens (Novo Nordisk). The study drug (liraglutide and placebo) will 608 609 delivered in identical prefilled pens, labeled with serial numbers and accompanied by a 610 dispensing unit list. Printed directions for use of the medication will be handed out to subjects before administration of trial drug. All patients will receive the same instructions on how to 611 612 take the medicine. As investigators and participants are blinded to drug assignment, an independent unblinded research assistant will instruct the investigators as to which serial 613 614 numbers to supply each woman with. The participants will be randomized in a 2:1 ratio (liraglutide: placebo), as we believe that this will facilitate the recruitment to the study. 615

B. *Treatment*- all patients will be dispensed 5 months (18 weeks) of liraglutide 3 mg (LIRA 3
mg) treatment or placebo and 4 home pregnancy test kits.

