For all analyses, in which the measures are continuous, data from evaluable subjects will be submitted to a repeated-measures general linear model (SS/ Drug treatments x repeated measures ANOVA) including the arm of drug treatment (liraglutide 3mg vs. placebo) as the between-subjects effect, and the visit (baseline and 30 wks) as the within-subjects effect. To evaluate the differences in the response to each treatment over visits, the interaction effect will be calculated. Baseline comparisons between groups will be made by one-way ANOVAs.

Frequency of patients achieving a body weight reduction of at least 5% and 10% before and after treatment will be compared with the McNemar test (complex chi square $[\chi^2]$ for paired data), which formally tests for a change between the observed proportions of k related samples. Dysglycemia occurrence before and after different treatment will also be compared with the McNemar test. The difference in frequency of menstruation before and aftertreatment will also be compared using the McNemar test.

Data will be analyzed on completed treatment parameters where relevant (evaluable population). The evaluable population is defined as all randomized subjects who complete treatment through week 30-32 week. Results will be reported as mean +/- S.E.M for normally distributed data and as median (interquartile range) if the distribution is not normal. Categorical data will be presented as percentage. P < 0.05 is considered statistically significant.

773

774 Sample Size and Justification

775 A priori sample size analysis was performed using the online calculator provided by the 776 Hospital Mallinckrodt General Clinical Massachusetts General Research Center (http://hedwig.mgh.harvard.edu/sample size/size.html). To calculate sample size, we used the 777 778 standard formula suggested for clinical trials by considering a type one error (α) of 0.05 and type 779 two error (β) of 0.20 (power = 80%). Sample size calculation revealed that 57 participants 780 randomized in a 2:1 ratio (liraglutide: placebo) were needed. Using a 30% drop-out rate, the 781 study is designed to recruit 92 patients, enroll 48 liraglutide and 24 placebo to ensure that the 782 number of subjects completing the study (38 LIRA/19 PL) as derived by the sample size 783 calculation is met.

784

785 Ethical and Regulatory Requirements

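### The models for free androgen index and the other hormonal and metabolic endpoints leave out baseline BMI and age; pre-specifying them is a cheap gain in precision

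*Combined protocol and SAP*

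**What the plan says.** Under Statistical Methods, every continuous endpoint goes into a repeated-measures model with arm between subjects and visit (baseline, week 30) within subjects. The treatment effect is the arm-by-visit interaction. No other covariate is named. For the groups at entry, the plan adds: "Baseline comparisons between groups will be made by one-way ANOVAs". It does not say what follows from the result.

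Under Study Assessments, A. Baseline, allocation uses computer-"generated random numbers using a block randomization method" in a 2:1 ratio, with no stratification factor. BMI is determined at the same pretreatment assessment. Key Inclusion Criteria admit women aged 18 to 45 and set a lower limit on BMI but no upper one.

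The introductory background, before Novelty of Study, has three relevant statements:

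- On metabolic risk in PCOS: "genetic background, personal and family history, degree of obesity must all be taken into account because they might aggravate or even trigger metabolic disturbances".
- On hormones: "Obesity significantly affects the circulating concentrations of total testosterone and SHBG". FAI is the ratio of these two.
- On metformin: it cites a result obtained "after adjustment for baseline BMI and age".

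**The concern.** BMI and age are known for every woman before allocation. The protocol itself links obesity to both components of a co-primary endpoint and cites earlier work that adjusted for BMI and age, yet the model uses neither. If either predicts the change in FAI, insulin or glucose measures, leaving it out adds unexplained variance to the treatment contrast in a trial sized for only 57 completers. In a trial where the arms happen to differ clearly on BMI, the unadjusted contrast also carries part of that difference.

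**Working it through.** **Inputs.** From Sample Size and Justification: 38 liraglutide and 19 placebo completers, alpha 0.05, power 80%. Assumed: a two-sided test, and a correlation r of 0.1 to 0.4 between the covariate and the change from baseline. The documents give no correlation.

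**1. The plan's own figure.** The 57 completers cannot be rebuilt forwards, because no effect size or SD is stated. Solved backwards, 38 versus 19 gives 80% power at a difference of 0.80 SD (noncentral t, 55 df). That is the benchmark below.

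**2. What the planned contrast already does.** With two visits, the arm-by-visit interaction is the same test as a two-sample t-test on change from baseline. It subtracts a difference in the outcome's own baseline, though regression to the mean leaves a remainder, which is a separate matter. A difference of d SD in another factor, such as BMI for FAI, is not subtracted. It shifts the contrast by r × d SD of the change.

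**3. How large chance imbalance gets.** The standardised baseline difference has SD sqrt(1/38 + 1/19) = 0.281.

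- P(|d| > 0.3) = 2[1 − Φ(0.3/0.281)] = 29%
- P(|d| > 0.5) = 2[1 − Φ(0.5/0.281)] = 7.5%
- The baseline ANOVA reaches significance only above t(0.975, 55) × 0.281 = 0.56 SD. An observed 0.5 SD difference gives P = 0.08.

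**4. Type I error given the imbalance.** The unadjusted statistic is approximately Normal with mean r × d/0.281 and variance 1 − r². At d = 0.5 the shift is 0.36 standard errors for r = 0.2 and 0.71 for r = 0.4. The chance of falling outside ±1.96 is:

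| r | d = 0 | d = 0.3 | d = 0.5 |
|---|---|---|---|
| 0.1 | 4.9% | 5.0% | 5.2% |
| 0.2 | 4.5% | 5.1% | 6.0% |
| 0.3 | 4.0% | 5.1% | 7.2% |
| 0.4 | 3.2% | 5.2% | 8.8% |

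Over all randomisations the error is 5% (0.049 to 0.051 in 40,000 simulated trials of 38/19).

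**5. Precision gained by adjusting.** Residual variance is multiplied by 1 − r². Power is taken from the noncentral t at 0.8/sqrt(1 − r²) with 55 − 2 = 53 df. The equivalent number of extra completers is 57/(1 − r²) − 57.

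| r | variance factor | power | extra completers |
|---|---|---|---|
| none | 1 | 80% | 0 |
| 0.1 | 0.99 | 80.2% | 0.6 |
| 0.2 | 0.96 | 81.4% | 2.4 |
| 0.3 | 0.91 | 83.4% | 5.6 |
| 0.4 | 0.84 | 86.2% | 10.9 |

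**The case against.** The case against is substantial, and most of it limits how far the point can go.

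- A reader might infer that the plan breaks its own rule, because the background says these factors must be considered. It does not. That sentence describes what aggravates metabolic disturbance in PCOS and says nothing about allocation or analysis. Its list does not include age or glycaemic status.
- A reader might infer that chance imbalance goes wholly uncorrected. It does not. The interaction subtracts each outcome's own baseline difference, and the weight co-primary is a percent change, already scaled to each woman's starting weight.
- A reader might infer that the treatment comparison is biased or its error rate inflated. Under randomisation it is neither on average. At 0.3 SD imbalance, which 71% of trials do not exceed, conditional error is about 5%.
- Unstratified block randomisation is valid in a trial of 72 women. The baseline ANOVAs are a poor guide to imbalance, but the plan gives them no role in the treatment comparison, so they cannot distort it.
- The statement about testosterone and SHBG concerns levels, whereas the contrast concerns change. A stable effect of BMI on level cancels in the subtraction. Only its correlation with change matters, and that is unknown.

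The last objection stands in full and is why the gain is shown as a range. None of the others is a reason to leave out covariates that are already recorded. Two considerations also favour naming them in advance. The analysis set is completers only with 30% dropout assumed, so differential dropout could add imbalance that randomisation does not cover. And pre-specification removes the temptation to adjust later for whichever baseline row turns out significant.

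**Conclusion.** The point holds as a low-cost improvement in precision. The plan is valid as written, but it ignores two covariates that it has in hand and that its own background suggests may matter. If BMI and age together correlate 0.2 to 0.4 with the change, adjustment is worth about 2 to 11 completers. At 0.1 it is worth practically nothing, and it does no real harm. Conditional type I error of about 6% to 9% applies at an imbalance of 0.5 SD, a size exceeded in only 7.5% of trials at 38/19, and it rests on the same assumed correlations.

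**What to change.** In Statistical Methods, pre-specify baseline BMI and age as continuous covariates in the between-arm models for FAI and the other hormonal and metabolic endpoints. In the two-visit model each covariate must enter with its interaction with visit, or equivalently the change is regressed on arm, BMI and age. A covariate entered only as a between-subjects main effect leaves the arm-by-visit contrast as it was. Make the change before unblinding.

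The cost is a sentence of SAP text and 2 of about 55 degrees of freedom, with no new data and no more patients.

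Two further changes are optional. Showing baseline values descriptively instead of testing them is tidier reporting. Stratifying the randomisation list by glycaemic status is a design choice with trade-offs at this sample size, not a required correction.

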- Surrogate measures of insulin action derived from 75 gram OGTT [insulin sensitivity index (HOMA-IR, Matsuda index), corrected early insulin secretory response (insulinogenic index/HOMA-IR), area under the curve (AUC) for insulin and glucose, and oral disposition index (product of Matsuda index and insulinogenic index; SI_{OGTT} x Δinsulin 30–0 min to
- 408 glucose 30–0 min)]

- 409 Cardiovascular Risk Factors (change from baseline to 30 weeks)
- 410 1. Plasma lipid fractions
- 411 2. Blood pressure
- 412 Other endocrine levels (change from baseline to 30 weeks)
- 413 1. Adrenal androgen concentration- dehydroepiandrosterone sulfate (DHEAS) levels
- The following will be documented for each patient:
- Presence of polycystic ovary syndrome (PCOS) will be recorded using modified National Institutes of Health (NIH) criteria which are inclusive of presence of oligo-/amenorrhea (cycle >35 days or <8 cycles year), and clinical and/or biochemical hyperandrogenism, after exclusion of related disorders. Other causes to bleeding irregularities and androgen excess will be excluded.
- 2. Metabolic syndrome (MetS) will also be documented and defined (2005 National Cholesterol Education Program, Adult Treatment Panel III) as the presence of at least three of the following criteria: abdominal obesity (waist circumference >80 cm in women); serum triglycerides ≥1.7 mmol/L; serum HDL <1.3 mmol/L; systolic blood pressure ≥130 mmHg and/or diastolic blood pressure ≥85 mmHg; and fasting plasma glucose ≥7.0 mmol/L
- 426

427 Safety variables/Measures

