- BMI ≥30 kg/m2 or BMI ≥27 kg/m2 with one or more obesity-associated co-morbid
 conditions (e.g. hypertension, and dyslipidemia)

- PCOS- NIH criteria hyperandrogenism and irregular menstrual cyclicity
- Non-diabetic as determined by a 75 gram oral glucose tolerance test (OGTT) and
 hemoglobin A1C. Non-diabetic is inclusive of women with impaired fasting glucose (IFG),
 impaired glucose tolerance (IGT), or both (IFG/IGT). Participants with diabetes will be
 excluded
- Willing to use effective contraception consistently during therapy which is defined as:
- 487
- 488

an intrauterine device, tubal sterilization, or male partner vasectomy, or
 combination of two barrier methods with one being male condom.

[figure not shown]
• Written consent for participation in the study

490 Key Exclusion Criteria

- Presence of significant systemic disease, cerebrovascular disease, clinically significant
 cardiac abnormalities or heart problems including congestive heart failure, unstable
 angina or acute myocardial infarction, current infectious liver disease, acute stroke or
 transient ischemic attacks, history of pancreatitis, or diabetes mellitus (Type 1 or 2)
- Any hepatic diseases in the past (infectious liver disease, viral hepatitis, toxic hepatic damage, jaundice of unknown etiology) or severe hepatic insufficiency and/or significant abnormal liver function tests defined as aspartate aminotransferase (AST) >3x upper limit of normal (ULN) and/or alanine aminotransferase (ALT) >3x ULN
- Renal impairment (e.g., serum creatinine levels ≥1.4 mg/dL for women, or eGFR <60
 mL/min/1.73 m2) or history of unstable or rapidly progressing renal disease or end stage
 renal disease.
- Uncontrolled thyroid disease (documented normal TSH), Cushing's syndrome, congenital
 adrenal hyperplasia or clinically significant elevations in prolactin levels. The clinical
 significance of prolactin levels will be determined by the treating physician
- Significantly elevated triglyceride levels (fasting triglyceride > 400 mg %)
- Untreated or poorly controlled hypertension (sitting blood pressure > 160/95 mm Hg)
- Use of hormonal medications, the use of medications that cause clinically significant
 weight gain or loss (prescription or OTC) and medications known to exacerbate glucose
 tolerance (such as isotretinoin, hormonal contraceptives, GnRH analogues,

510	glucocorticoids, anabolic steroids, C-19 progestins) including herbal medicines for at least

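### The metabolic-syndrome glucose component (fasting glucose ≥7.0 mmol/L) is probably unreachable at entry in a trial that excludes diabetes and admits impaired fasting glucose, so baseline MetS is likely to be under-recorded

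*Combined protocol and SAP*

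**What the plan says.** The list of items to be documented for each patient, at the end of Efficacy Variables/Measures, has MetS as its second item: "Metabolic syndrome (MetS) will also be documented and defined (2005 National Cholesterol Education Program, Adult Treatment Panel III"). The rule is a count over five components: waist circumference, triglycerides, HDL, blood pressure and fasting glucose. It is worded "as the presence of at least three of the following criteria". The list closes with "diastolic blood pressure ≥85 mmHg; and fasting plasma glucose ≥7.0 mmol/L".

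Eligibility runs the other way. The Key Inclusion Criteria name the test that settles diabetes status, "Non-diabetic as determined by a 75 gram oral glucose tolerance test (OGTT) and" a second measure, HbA1c. A further sentence there reads "Non-diabetic is inclusive of women with impaired fasting glucose (IFG"); IGT, alone or with IFG, is treated in the same way. The Key Exclusion Criteria list "history of pancreatitis, or diabetes mellitus (Type 1 or 2"). The baseline assessment under Study Assessments takes glucose at 0, 30, 60 and 120 minutes before randomization, partly to assess diabetes. One fasting sample therefore serves both screening and the MetS component.

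The background section describes the syndrome as a cluster that includes hypertension and "elevated triglycerides, low high-density lipoprotein cholesterol, glucose intolerance, and obesity". It gives separate prevalences in PCOS for IGT (30–40%) and type 2 diabetes (7.5–10%).

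The documents state no fasting cut-off for diabetes and none for IFG.

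**The concern.** The glucose component seems to be set at a level that the entry criteria remove. If so, one of the five components is fixed at zero for every randomized woman at baseline. The women with IFG, whom the trial deliberately admits, get no credit for the abnormality that the background section treats as part of the syndrome.

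At stake is the baseline description of cardiometabolic risk in a trial whose rationale is insulin resistance. Recorded MetS prevalence would be too low. It would also not be comparable with the 33–47% that the background cites for women with PCOS, if that figure counts glucose intolerance.

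**Working it through.** The plan has no calculated figure to reproduce here. The check has three parts: a unit conversion, a comparison of two rules, and an illustration of size.

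**1. Unit.** 7.0 mmol/L × 18.016 = 126.1 mg/dL.

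**2. Overlap of the two rules at entry.** Let c be the fasting value at or above which the site calls a woman diabetic and excludes her. Eligible women then have fasting glucose below c, and the MetS component needs 7.0 or more. Values of c are assumed, because the documents give none.

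| Assumed c (mmol/L) | Eligible values that also score |
|---|---|
| 6.5 | none |
| 7.0 | none |
| 7.5 | 7.0 to <7.5 |
| 7.8 | 7.0 to <7.8 |

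At any c of 7.0 or below the overlap is empty. Three of five becomes three of four, and all women with IFG score negative on glucose. The overlap opens only if c is above 7.0, or if the fasting value alone is not enough to exclude.

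**3. Size.** If IFG were counted, a woman with IFG would change overall MetS status only when she has exactly two of the other four components. With g the proportion with IFG and P2 the probability of exactly two of the other four:

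women changed = 72 × g × P2

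The 72 is the planned number randomized. All prevalences below are assumed, and components are taken as independent of each other and of IFG.

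- *Low case.* Waist 95%; triglycerides, HDL and blood pressure 20% each. P2 = 0.95 × 3 × 0.20 × 0.80² + 0.05 × 3 × 0.20² × 0.80 = 0.3648 + 0.0048 = 0.370. With g = 10%: 72 × 0.10 × 0.370 = 2.7.
- *Middle case.* Waist 100%; the other three 35% each. P2 = 3 × 0.35 × 0.65² = 0.444. With g = 30%: 72 × 0.30 × 0.444 = 9.6.
- *High case.* Waist 100%; triglycerides 25%, HDL 55%, blood pressure 25%. None of the three: 0.75 × 0.45 × 0.75 = 0.253. Exactly one: 0.084 + 0.309 + 0.084 = 0.478, which is P2 here. With g = 20%: 72 × 0.20 × 0.478 = 6.9. With g = 40%: 72 × 0.40 × 0.478 = 13.8.

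In the high case, MetS prevalence as written is 1 − 0.253 − 0.478 = 0.269, about 19 of 72. Counting IFG gives 0.269 + 0.20 × 0.478 = 0.364 (26 of 72) up to 0.269 + 0.40 × 0.478 = 0.460 (33 of 72).

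The span is about 3 to 14 women. The share of women with IFG whose overall status changes is 37% to 48%. The direction does not depend on these inputs: a component held at zero can only lower the count.

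**The case against.** The strongest reply is that little depends on this variable. MetS is not a primary or secondary endpoint, an entry criterion or a randomization factor, and Statistical Methods lists no test for it. Its ingredients are all recorded, so it can be re-derived later under any definition. This stands, and it limits the point to a descriptive variable.

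Several stronger readings are tempting but not supported:

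- *That exactly 0 of 72 women can score the component.* This depends on a diabetes cut-off that the documents do not give. They also do not say how OGTT and HbA1c results are combined when they disagree.
- *That all women with IFG are misclassified on MetS.* They are negative on the glucose component. In the illustrations, more than half keep the same overall status.
- *That improvement from IFG to normal would be lost at week 30.* No section schedules MetS at week 30. Fasting and 2-hour glucose are secondary endpoints, and dysglycemia before and after treatment has its own planned comparison.
- *That the 7.0 limit departs from the cited 2005 definition.* The source is not available here, so this cannot be checked.
- *That the waist limit, "abdominal obesity (waist circumference >80 cm in" women, is met by nearly everyone.* The documents give no waist distribution. The 95–100% used above is an assumption.

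It is also fair to say that glucose intolerance is broader than IFG. Women with IGT alone would still score negative under any fasting criterion, and the documents give no IFG prevalence.

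**Conclusion.** The inconsistency is real but minor. If the site excludes women at a fasting glucose of 7.0 mmol/L or lower, the glucose component cannot be met at entry, the rule reduces to three of four, and women with IFG score negative on a component that the protocol's own background describes as glucose intolerance. Baseline MetS is then under-recorded for women with IFG who have exactly two other components, illustratively about 3 to 14 of 72.

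The empty overlap rests on the assumed cut-off. The count rests on assumed, independent prevalences, with IFG at 10–40%. The primary and secondary analyses and the sample size are not affected. The definition should still be corrected, because a stated rule that is followed as written would give the wrong classification for some women.

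**What to change.** In the MetS item under Efficacy Variables/Measures, replace the fasting glucose limit of 7.0 mmol/L with the fasting cut-off used to classify IFG at entry. Check the result against the cited 2005 definition. State that IFG cut-off and the fasting cut-off for diabetes in the Key Inclusion Criteria, since neither is given now and the two sections cannot be reconciled without them. Apply the corrected component to the baseline fasting sample, and to the final-visit sample if MetS is summarized then.

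The cost is one changed threshold and two stated cut-offs. Fasting glucose is already measured at both visits, so no sample, visit or test is added. Reported MetS prevalence will be higher than under the present wording.
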